### 12.2 Analysis Plans

If the trial is stopped early, this drug will not be considered of interest for future study VHL patients. If all 40 patients are accrued, we will estimate the response rate, early progression rate, toxicity rate and their corresponding 95% posterior credible intervals.

Biomarker endpoints and genetic mutations will be measured at baseline and/or over time. Summary statistics, including frequency tabulation, means, standard deviations, median, and range, will be used to describe subject characteristics and marker data. The chi-squared ( $\gamma^2$ ) test or Fisher's exact test will be used to test the association between two categorical variables, such as response and prognostic factors and discrete markers. The association among various continuous and discrete markers and response may be assessed first by the exploratory data analysis graphically and tested using Wilcoxon rank sum test. Correlation among continuous biomarkers will be examined by Pearson or Spearman rank correlation coefficients. Both univariate and multivariate logistic regressions may be performed to model the baseline prognostic factors such as age, gender, race, smoking history, performance status, markers, etc, on response, when appropriate. We will also use the generalized estimating equations to model correlated discrete variables. Repeated measures analysis including mixed effects model will be performed to analyze continuous biomarkers change over time. Time to progression (TTP) will be estimated using the Kaplan-Meier method. Log-rank test will be performed to test the difference in survival between prognostic groups. Regression analyses of survival data based on the Cox proportional hazards model will be

Protocol 2011-0465 ASeptember 6, 2017 Page 49 of 50

conducted on TTP. The proportional hazards assumption will be evaluated graphically and analytically, and regression diagnostics (e.g., martingale and Shoenfeld residuals) will be examined to ensure that the models are appropriate.

Table 2. Operating characteristics for the stopping rules for excessive PD rate or DD rate

True PD Rate	True DD Rate	Probability of	Average Expected #
		Early	of Patients
		Termination	
0.10	0.05	0.03	39.2
0.30	0.05	0.57	25.8
0.20	0.10	0.27	33.1
0.30	0.10	0.61	24.6
0.30	0.15	0.71	22.1
0.10	0.20	0.64	25.7
0.20	0.20	0.70	23.4
0.30	0.20	0.84	18.9
0.10	0.30	0.94	16.3

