#### 2.0 BACKGROUND

2.1 Von Hippel Lindau Syndrome

The VHL syndrome affects approximately 1 in 35000 live births each year worldwide. The disease results from an autosomal-dominant mutation associated with deletion of the *VHL* gene located on the short arm of chromosome 3. The VHL protein is directly responsible for downregulating hypoxia-inducible factor alpha (HIF) transcription factors responsible for several angiogenic responses to hypoxia. Thus, mutations of the VHL gene lead to the regulatory loss of HIF, with increased intracellular HIF during normoxia being the primary common pathway leading to the downstream manifestations of the syndrome via induction of VEGF, PDGF, erythropoietin, and a variety of other angiogenic pathways. The clinical presentation of this syndrome is characterized in late childhood and early adulthood by hemangioblastomas of the brain, spine, and retina, in addition to renal cell carcinoma, pheochromocytoma, neuroendocrine tumors of the pancreas, other benign tumors (e.g., endolymphatic sac tumors) as well as cystic lesions in various organs such as the kidneys and pancreas. Renal cell carcinomas and hemangioblastomas are directly related to HIF pathway activation, while pheochromocytomas appear to be induced via non-HIF pathways. The multi-organ morbidity of these lesions as well as their treatment is significant in these patients, who must often endure repeated, serial interventions of the CNS, eye, kidneys, pancreas, adrenal, and other organs. While little data has been published in regard to the multiplicity of interventions for all the involved organ systems, one report has shown that by age 30, most patients with VHL have had greater than 2 interventions for any involved organ. Of those with RCC, 88% required intervention at an average range of 1.4 to 3 interventions per year. Renal and CNS tumors comprise the majority of those causing

Protocol 2011-0465 ASeptember 6, 2017 Page 6 of 50

the greatest impact, as does their treatment.

Genetic characterization of the various mutations has been classified as Type 1 (no pheochromocytoma) and Type 2 (presence of pheochromocytoma) which is further characterized into 2a, low risk of renal cancer, 2b, high risk of renal cancer; and 2c, pheochromocytoma only.

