## Table 1. Best Response of von Hippel-Lindau Lesions by RECIST after Sunitinib

Abbreviations: RECIST, Response Evaluation Criteria in Solid Tumors; NET, neuroendocrine tumors.

Of the 21 evaluable individual HB lesions, there were no partial responses (PR). In comparison, 6 of 18 RCC lesions responded with a PR, (P=0.014). All five pancreatic NETs responded with SD. None of the seven retinal angiomas demonstrated any shrinkage on ophthalmoscopy; however, two patients with retinal angiomas complained of increased hyperemia and eye discomfort during sunitinib treatment. When change in

Protocol 2011-0465 ASeptember 6, 2017 Page 10 of 50

lesion size was evaluated as a percentage by organ site per individual, RCC decreased a mean of 14.4% by the end of cycle four, NETs a mean 12.7%, and HB, 5.9% (Table 2). When size change was assessed as a continuous variable, both RCCs and NETs showed significant size decrease after four cycles of sunitinib therapy.

Forty-eight–week follow-up scans were obtained for renal lesions in five patients. In these patients, who had been finished with therapy for 6 months, RCC and NETs had regrown to close to baseline measurements but no larger (Table 2).

		Mean (Standard Error)						
	Baseline	Cycle 2	Percent	Cycle 4	Percent	Week 48	Percent	
Tumor Type	Size(cm)	Size (cm)	Change	Size (cm)	change	Size (cm)	change	
					-14.42		-3.37	
Renal Cell Carcinoma	2.41 (0.21)	2.04 (0.21)	-16.41 (3.9)	2.06 (0.22)	(4.5)	2.34 (0.24)	(5.7)	
P value		0.0004		0.0035		0.6098		
					-12.69		-1.72	
Pancreas NET	1.89 (0.28)	1.81 (0.28)	-3.59 (3.7)	1.64 (0.28)	(4.0)	1.89 (0.29)	(5.2)	
P value		0.284		0.011		0.959		
Hemangioblastoma	0.81 (0.08)	0.81 (0.08)	0.65 (3.4)	0.76 (0.08)	-5.9 (5.4)	0.76 (0.09)	-6.2 (5.4)	
P value		0.8	350	0.2	80	0.32	0	

Table 2. Mean Change from Baseline in Size of von Hippel-Lindau Lesions after Treatment with Sunitinib.	Table 2. Mean Change	e from Baseline	n Size of von	Hippel-Lindau	Lesions after	Treatment with Sunitinib.
---	----------------------	-----------------	---------------	---------------	---------------	---------------------------

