#### 2.4 Rationale for Current Study:

In our previous study we found that sunitinib, an oral small-molecule inhibitor of VEGFR, PDGFR, Flt3, and cKit, provides a consistent response in RCCs but not in CNS hemangioblastomas from patients with VHL. Endothelial VEGFR and FGFR are expressed differently in RCCs and HBs. Based on these observations, we would like to further expand our observations in VHL patients with measurable VHL lesions. We predict that pazopanib, an orally bioavailable small molecule inhibitor of VEGFR as well as other receptor tyrosine kinases, will provide at least the same benefit as sunitinib in a broad VHL patient population, but may provide superior overall quality of life. Phase III studies and MD Anderson Cancer Center clinical experience with pazopanib suggests that this agent may result in fewer toxicities when compared with sunitinib. As individuals with VHL need to balance the impact of disease progression on their overall outlook with the possible consequences of being on chronic therapy which produces continuous side effects, pazopanib may be an acceptable choice. In addition, although our initial clinical and tissue based observations suggest that sunitinib did not provide any clear shrinkage of hemangioblastomas in our clinical study, these observations require further validation. For this reason, we have chosen to proceed with a larger single arm study evaluating pazopanib in the treatment of patients with VHL, but will not exclude individuals with hemangioblastomas, nor will we make it a requirement for individuals who enroll on this study to have RCC.

Protocol 2011-0465 ASeptember 6, 2017 Page 13 of 50

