2.6 Rationale for choice of preclinical endpoints

Data on circulating cytokine and angiogenic factors suggest these factors provide important prognostic and potential predictive information in patients with RCC. Little is known about how these factors vary as a function of lesion type in VHL at baseline, and whether they predict for benefit from pazopanib therapy. We will collect circulating cells, plasma and sera from patients at baseline, after 12 weeks, 24 weeks and at time of study discontinuation.

It is not known whether specific VHL mutations are associated with response to pazopanib in VHL patients. We will perform exploratory analyses of the relationship between VHL genotype and response to therapy, both globally and according to specific lesion.

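### Section 12.2 tests markers and genotype against response without naming tumour type, so a pooled association could reflect who has a renal tumour rather than who is sensitive to the drug

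*Combined protocol and SAP*

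**What the plan says.** Section 12.2 (Analysis Plans) assigns chi-squared or Fisher tests to response against prognostic factors and discrete markers, and the Wilcoxon rank sum test to continuous markers against response. Logistic regression is optional and would model baseline factors "such as age, gender, race, smoking history, performance status, markers, etc, on response". GEE is named for correlated discrete variables. No test is stratified, and neither tumour type nor organ appears.

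Other sections bear on this:

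- Section 2.6 plans the genotype work at two levels: "We will perform exploratory analyses of the relationship between VHL genotype and response to therapy, both globally and according to specific lesion". It also says that little is known about how circulating factors vary with lesion type.
- Section 9.1 aims at genetic signatures of response at organ level. Sections 11.1.5 and 11.3.1 score response separately by organ.
- Section 2.1 divides VHL Type 2 into "2a, low risk of renal cancer, 2b, high risk of renal cancer; and 2c, pheochromocytoma only".
- Section 2.3.1 reports the sunitinib experience: "In comparison, 6 of 18 RCC lesions responded with a PR", with none in 21 hemangioblastomas. Section 2.4 summarises that sunitinib "provides a consistent response in RCCs but not in CNS hemangioblastomas from patients with VHL". It then opens this trial to patients without renal cell carcinoma.
- Response is CR+PR in Section 12.1, but CR+PR+SD in the note to Section 11.3.3.

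**The concern.** In the protocol's own data, tumour type is the strongest known predictor of partial response, and enrolment is deliberately mixed. Suppose a cytokine or endothelial-cell count differs between patients with and without renal tumours for reasons unrelated to treatment. In a pooled test it will then tend to differ between responders and non-responders as well, because the responders will mostly be renal patients. The test cannot separate that pattern from a marker that predicts benefit.

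Genotype raises a related question of interpretation. If some VHL types lead more often to renal tumours, a global association with response may arise with no difference in drug sensitivity between genotypes once tumour type is held fixed.

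At stake is the reading of both preclinical objectives in Section 1.2: circulating factors under treatment, and genotype against response.

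**Working it through.** **Step 1. The link between tumour type and response.** By lesion counts in the Section 2.3.1 table, PR occurred in 6/18 = 33% of renal cell carcinomas. Elsewhere it was 0/21 + 0/9 + 0/7 + 0/5 + 0/3 = 0/45. I use counts, because the printed renal percentages for SD and PD (67% and 10%) do not match 10/18 = 56% and 2/18 = 11%. The stated P=0.014 for 6/18 v 0/21 is not reproduced exactly: Fisher gives 0.0057, Pearson 0.0040, Yates-corrected 0.0151, and chi-squared on PR/SD/PD 0.0135. The test used is not stated, and all of these support the same conclusion.

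**Step 2. Markers.** Assumptions not in the documents: 40 patients; renal tumour present with a given probability; response 1/3 if renal and 0 otherwise; marker standard normal, plus 1 SD if renal; no relation between marker and response within tumour type; two-sided 0.05. By simulation, the Wilcoxon test of responders against non-responders rejects:

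- pooled: about 14% of the time when 70% of patients are renal, rising to about 23% when 40% are;
- stratified by renal tumour (van Elteren): about 5%;
- within renal patients only: about 4% to 5%.

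**Step 3. Genotype, global test.** Assumptions not in the documents: two genotype groups of 20, one tumour type per patient, the same response rates, no genotype effect within tumour type. Group response is p = (renal share) × 6/18. The rejection rate is the sum over a, b of Bin(a; 20, p1) × Bin(b; 20, p2) for all tables with Fisher P ≤ 0.05.

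| Renal share | p1 v p2 | Odds ratio | Pooled Fisher rejects |
|---|---|---|---|
| 50/50 | 16.7% v 16.7% | 1.0 | 2% |
| 60/40 | 20.0% v 13.3% | 1.6 | 4% |
| 70/30 | 23.3% v 10.0% | 2.7 | 12% |
| 80/20 | 26.7% v 6.7% | 5.1 | 28% |
| 90/10 | 30.0% v 3.3% | 12.4 | 54% |

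For example, at 80/20: 0.8 × 0.333 = 0.267 and 0.2 × 0.333 = 0.067; odds ratio (0.267/0.733)/(0.067/0.933) = 5.1. Uncorrected chi-squared rejects 5%, 20%, 41% and 69% at 50/50, 70/30, 80/20 and 90/10. An exact test stratified by tumour type (20,000 simulated trials) rejects 2.4%, 1.9%, 1.5% and 0.7% at the same four shares.

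**Step 4. Dependence on the response definition.** Under CR+PR+SD the same lesions give (6+10)/18 = 16/18 = 89% and 19/21 = 90%, Fisher P = 1.0. The pooled genotype test then rejects about 1.3% of the time at 70/30 to 90/10. The problem exists only under CR+PR.

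**Step 5. What stratification costs.** If non-renal patients never respond, only the renal stratum carries information. At 80/20 that is 16 v 4 patients. An exact test there has 7% power for response of 50% v 10%, or 33% if the higher rate falls in the group of 4.

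**The case against.** The strongest reply is that the plan already thinks by organ. Section 9.1 puts the genotype signatures at organ level, Section 2.6 includes lesion-specific analysis, and Sections 11.1.5 and 11.3.1 score response by organ. That stands, and it answers much of the genotype question. It does not cover the marker tests, for which no organ-level response analysis is planned, and 12.2 does not carry it into any test.

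A reader might infer that tumour type confounds the genotype test. The documents do not support that. VHL genotype is germline and precedes the tumours, so tumour type lies on the path from genotype to response. A global association would be a genuine total effect; the rejections in Step 3 are errors only if it is read as drug sensitivity within tumour type.

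A reader might also infer that the documents tie circulating markers to renal tumours. They do not: Section 2.6 says little is known, and the tissue results in Section 2.3.2 concern receptors in tumour specimens, not blood. The 1 SD shift is an assumption. So are the renal shares: Section 2.1 attaches renal risk only to the Type 2 subclasses, and no section gives the tumour mix. Inflation is small until the imbalance is marked (4% at 60/40).

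Three further points stand. The covariate list is illustrative and the models optional, so tumour type is unnamed rather than excluded. The response rates are per lesion and from sunitinib, not per patient on pazopanib. Section 2.6 calls the genotype work exploratory.

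**Conclusion.** The concern holds as a gap in Section 12.2 under the CR+PR definition. For markers, the unadjusted tests could mistake a marker of renal tumour for a predictor of response, with rejection of about 14% to 23% instead of about 5% if the marker is 1 SD higher in renal patients. For genotype, the pooled result cannot be read as genotype-specific sensitivity, and 12.2 does not implement the organ-level plan set out elsewhere.

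It would go too far to conclude that these analyses will return spurious associations. There is no inflation if renal share is equal across genotype groups, if a marker is unrelated to tumour type, or if response counts SD. All the rates above rest on assumed shares and shifts and on lesion-level sunitinib data, so they show scale only. The analyses are secondary to the main efficacy estimate, which this point does not affect.

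**What to change.** In Section 12.2:

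1. Run genotype-response and marker-response tests within organ, or stratified by renal target lesion at baseline (yes/no): exact Cochran-Mantel-Haenszel for categorical factors, van Elteren for continuous markers.
2. For organ-level responses, use the GEE already named, with organ as a factor and clustering by patient.
3. Use exact or penalised logistic regression where a stratum has no responders. Ordinary maximum likelihood gives no finite estimate for the renal term in that case, and an organ without responders raises the same difficulty in the GEE.
4. Label pooled global tests as descriptive.
5. State which response definition these tests use, and reconcile the note to Section 11.3.3 with Section 12.1.

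No new data are needed, since Section 11.1.3 already records target lesions at baseline. The cost is more than one degree of freedom: strata without responders add nothing, and power in the renal stratum is low (7% to 33% in the example above). Results should therefore be reported as estimates with intervals. Whether the kidney result should lead is the sponsor's choice. Section 2.4 also wants the hemangioblastoma findings validated, so nothing here requires it.
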